Subjects will complete validated standardized quality of life questionnaires and pelvic floor muscle testing using the PFDx device at in-office visits at baseline, 4 weeks and 8- weeks. They will record 3-day voiding diaries at baseline and at 8-weeks. Beyond 8- weeks subjects will be asked to participate in follow-up calls at 6 and 12 months and complete validated standardized quality of life questionnaires by mail or email. Patients who were randomized to the Leva arm of the study and were sub-randomized to the “follow up reminder” will receive weekly reminders to perform their pelvic floor exercises using the Leva device

The study will be funded by Renovia, who will provide leva Plus and PFDX devices for the study and subject re-numeration.

\$50 for the baseline visit with the study team
\$50 for the 4-week follow up visit
\$100 for the 8-week final study visit
\$50 for the completion of >80% of the study exercises
\$50 upon completion and return of surveys at 6 months
\$50 upon completion and return of surveys at 12 months.

Please note that \$300 compensation is provided for every subject who completes the study in its entirety. This compensation level will increase to \$350 for those subjects in either arm who attest to completion of >80% of the study exercises.

Initial payment will occur by the site and in a manner consistent with individual site policy after the completion of the 8-week final study visit. Compensation will occur immediately following the return of completed 6-month and 12-month surveys.

If the subject leaves study early, the subject will receive a pro-rated amount based on the study milestones completed. Subjects will be compensated \$25 for unscheduled return visits.

Subjects will be reimbursed for parking costs associated with their visits.

Visit #1 – Baseline visit - the participants will undergo the following procedures:

Following completion of baseline evaluation and consent, patients will be randomized by study coordinators at the baseline office visit using an automated randomization system.

- 1) Medical history including GYN history, OB history, medical diagnoses, medications, and prior surgical procedures.
- 2) Questionnaires:
 - a. PFDI
 - b. PISQ-IR
 - c. McGill Pain Questionnaire
 - d. SESPPFE
 - e. Patient Global Impression of Severity (PGI-S) Scale
 - f. WHODAS

- g. PFIQ
- 3) Voiding diary – collection of a 3-day intake and output and symptoms diary completed *before* baseline visit

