- Subjects randomized to the leva® Plus Pelvic Digital Health System will receive training on the use of the Leva® Plus Digital Health System including installation of the Digital Health System app, the completion of a training module, a timed lift test and one full leva exercise session of five timed lifts. Training will occur at the baseline visit. Subjects will be instructed to perform the lifts twice a day, for 2 ½ minutes each session, 7 days a week for a total of 8- weeks. Subjects will be informed they will be asked to attest to the fact that they performed these exercises twice daily at least 80% of the time (approximately 11 times per week). This attestation will ask the subject to recall their

adherence; no diary or other record will be required, although they will also be informed that the leva digital system tracks adherence. During the study period (8-weeks) subjects with the leva will contact the Renovia Patient Care Engagement team with any technical questions or issues regarding leva use. They will receive regular (6 days/week) text messages based on their performance of pelvic floor muscle exercises using the Leva device using predetermined algorithm for content. For any clinical questions they will be directed to their physician's office to speak with a healthcare provider.

- Subjects will return to the office on week 4 to participate in validated questionnaires (see chart) and undergo progress evaluation using the PFDx device. For clinical questions they will be directed to follow up with their physician. Their evaluator will be blinded to their randomization.
- Subjects will return to the office on week 8 to participate in validated questionnaires (see chart) and undergo progress evaluation using the PFDX device and physical examination including a POP-Q and Brinks score, and attest to their adherence. Their evaluator will be blinded to their randomization.
- Following week 8, patients will be recommended to continue weekly pelvic floor muscle exercises using the leva device but will be free to pursue alternative treatments if desired. Based on initial sub-randomization, subjects will receive periodic standardized text messages reminding them to use the leva over the next 10 months or receive no additional contact via the leva device.

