- At 6- and 12- months they will participate in validated questionnaires (see chart) by phone and email or mail, in addition to reporting what (if any) additional therapies they have undergone for treatment of stress urinary incontinence at 6 months and 12 months after baseline.
- The third party research center will provide a single phone call to the subjects receiving the leva plus to ensure the device is functioning properly. If there are questions regarding the device function, a conference call will be undertaken to allow the subject to trouble-shoot device function with the sponsor technical specialist. The sponsor will at no time possess protected health information (PHI)

VISIT CONTENT

At week 4 all study participants will return to the office to undergo a PFDx evaluation of pelvic floor muscle function and complete and return the following questionnaires:

- a. PFDI
- b. PISQ-IR
- c. McGill Pain Questionnaire
- d. SESPPFE
- e. Patient Global Impression of Severity and improvement (PGI-S, PGI-I) Scale
- f. WHODAS
- g. PFIQ

At week 8 all study participants in both arms will return to the clinic for the PFDx device evaluation of pelvic floor muscle function and physical examination including a POP-Q and Brinks score, and the following questionnaires:

- a) PFDI
- b) PISQ-IR
- c) McGill Pain Questionnaire
- d) SESPPFE

- e) PGI-S and PGI-I
- f) WHODAS
- g) PFIQ
- h) Attestation of 80% or greater compliance with exercises twice daily as per protocol

The 6 and 12 months follow-up by phone and email or mail will include:

- i) PFDI
- j) PISQ-IR
- k) McGill Pain Questionnaire
- l) SESPPFE
- m) PGI-S and PGI-I
- n) WHODAS
- o) PFIQ

PFDx device pelvic floor muscle evaluation for both study arms will include:

- Baseline pelvic floor muscle vaginal angle (at rest)
- Pelvic floor muscle vaginal angle with Valsalva
- Pelvic floor muscle angle with relaxation
- Pelvic floor muscle angle with muscle contraction
- Number of repetitions of contraction in 15 seconds;
- Maximum time a subject can sustain a pelvic floor muscle contraction.

This evaluation will be conducted using the PFDx device placed in the vagina by the subject and conducted by study staff using an automated measurement protocol.

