3.3 Compliance

Compliance will be assessed by participant report at the 8-week study visit. Participants who report performing the exercises at least 80% of the time will be considered compliant. Exercises using the leva[®] Plus Pelvic Digital Health System should be performed twice daily, for a total of 14 times per week; therefore, participants who perform the exercise at least 11 times per week will be considered compliant. Exercises in the control (Kegel) arm should be performed three times per day, for a total of 21 times per week; therefore, participants who perform the exercises 17 times per week will be considered compliant.

In addition, for participants in the leva[®] Plus Pelvic Digital Health System arm, self-report will be validated using data from the device. The distribution of concordance will be reported. Allowing for some error in reporting, reports within 1 exercise per week (over or under report) will be considered concordant. This may be altered based on the data, at which point the statistician and investigators may re-define concordance.

3.4 8-week assessment

The primary outcome, 8-week assessment, will be reported as described below. Efficacy will also be reported as both improvement on the PGI-I and no urinary distress on the PFDI-20. In addition, the results of the PFDI, PISQ-IR, McGill Pain Questionnaire, SESPPFE, WHODAS, PFIQ, PGI-S and clinical assessment of urinary incontinence (voiding diary, POP-Q, PFDx device assessment) will be reported.

Efficacy of leva[®] Plus Pelvic Digital Health System: Two definitions of efficacy will be reported as two “primary” outcomes. Both will be dichotomous (yes or no). Efficacy will be assessed at the 8-week visit and will be defined as: 1, improvement of symptoms, and 2, no urinary distress.

- “Improvement” will be defined as “much better” or “very much better” on the Patient Global Impression of Improvement (PGI-I) scale. Any other answers will be considered “No improvement”.
- “No urinary distress” will be defined as a raw score of 2 or less on all six indicators in the Pelvic Floor Disability Index (PFDI-20) Urinary Distress Inventory (UDI-6) subscale. Raw scores of greater than 2 will be considered reports of distress.

Both will be reported as the primary study outcome.

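### The SAP's leva compliance cut-off of 11 of 14 sessions per week is 78.6% and fails its own 80% rule; the Kegel denominator also needs reconciling

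*SAP*

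**What the plan says.** SAP 3.3 states the general rule first: "Participants who report performing the exercises at least 80% of the time will be considered compliant". It then turns the rule into weekly counts. Leva exercises "should be performed twice daily, for a total of 14 times per week", from which it concludes that "participants who perform the exercise at least 11 times per week will be considered compliant". Kegel exercises "should be performed three times per day, for a total of 21 times per week", from which it concludes that "participants who perform the exercises 17 times per week will be considered compliant".

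Protocol 8.1 carries the same counts, but loosely. Under the leva arm, women are told that they will attest to exercising "twice daily at least 80% of the time (approximately 11 times per week". The Kegel arm text has a matching sentence with about 17 per week. That sentence also says twice daily, although the regimen described in the same paragraph is three times daily. The week-8 item under Visit Content, which applies to both arms, reads "Attestation of 80% or greater compliance with exercises twice daily as per protocol". Protocol 8.4.1 says that both groups train twice daily.

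**The concern.** The SAP presents the count of 11 as a consequence of the 80% rule, and it is not one. SAP 3.3 therefore holds two operative definitions that classify the same leva participant in opposite ways. The protocol's count was an approximate gloss; the SAP dropped the qualifier and made 11 a hard cut-off.

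Evaluating compliance in the leva arm is one of the three objectives in SAP section 1, and the slip can only raise the reported leva rate. Eleven is also the number that leva women were given at baseline, so reports of exactly 11 are plausible.

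The Kegel arm has a different problem. Its percentage cannot be calculated until the documents agree on how many sessions were prescribed.

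**Working it through.** **Inputs.** Threshold 0.80; leva 14 sessions per week, cut-off 11; Kegel 21 sessions per week, cut-off 17 (all SAP 3.3). Duration 8 weeks (Protocol 8.1). 30 women per arm (SAP section 2).

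**1. Reproducing the plan's counts.**
- Leva: 0.80 × 14 = 11.2, nearest whole number 11.
- Kegel: 0.80 × 21 = 16.8, nearest whole number 17.

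Both stated counts come out by rounding to the nearest integer. Rounding up would give 12 and 17; rounding down, 11 and 16. Only nearest-integer rounding gives the stated pair, and a minimum of 80% does not allow rounding down from 11.2.

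**2. Testing the counts against the rule.**

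| | Leva | Kegel (21 per week) |
|---|---|---|
| Cut-off / prescribed, weekly | 11/14 = 78.6% | 17/21 = 81.0% |
| Cut-off over 8 weeks | 88 of 112 | 136 of 168 |
| 80% over 8 weeks | 89.6 | 134.4 |
| Meets 80%? | No | Yes |
| Smallest 8-week total that meets it | 90 (80.4%) | 135 (80.4%) |

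The leva cut-off is 80.95 − 78.57 = 2.4 percentage points looser than the Kegel cut-off.

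**3. How many women could change class.** The documents give no distribution of adherence. Assume that weekly reports are whole numbers and roughly normal with SD 2. The share at exactly 11 is then Φ((11.5 − mean)/2) − Φ((10.5 − mean)/2).
- Mean 8: Φ(1.75) − Φ(1.25) = 0.960 − 0.894 = 0.066, or 2.0 of 30.
- Mean 11: Φ(0.25) − Φ(−0.25) = 0.599 − 0.401 = 0.197, or 5.9 of 30.
- Mean 13: Φ(−0.75) − Φ(−1.25) = 0.227 − 0.106 = 0.121, or 3.6 of 30.

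The range is about 7% to 20%, or 2 to 6 of 30. For a given SD, a mean of 11 is the worst case.

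**4. The Kegel denominator.**
- Three times daily: 3 × 7 = 21 per week (SAP 3.3; regimen in the Kegel arm text of Protocol 8.1).
- Twice daily: 2 × 7 = 14 per week (attestation wording in the Kegel arm text, week-8 item in Visit Content, Protocol 8.4.1).

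Eighty percent of 14 is 11.2, so 12 or more sessions meet 80% of a twice-daily schedule, while the SAP asks for 17. A Kegel participant doing 12 to 16 sessions per week passes on the first basis and fails on the second. One who exercises exactly twice every day does 14 of 21, or 66.7%, by the SAP's count.

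**The case against.** The strongest reply is that this is harmless rounding. The shortfall is 11.2 − 11 = 0.2 session per week, and adherence is recalled without a diary. SAP 3.3 itself treats a self-report within one exercise per week of the device data as concordant. A leva woman doing 11 who followed the protocol's gloss would attest that she complied, and the SAP's count agrees with her. Compliance defines neither primary outcome (SAP 3.4) nor the analysis set, which is all randomized women (SAP 3.5).

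Most of that stands, and it keeps the point small. It does not remove it: the concordance tolerance governs agreement between report and device, not who is compliant, and SAP 3.3 still gives two answers for the same woman.

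A reader might infer more from three features of the documents, none of which bears the weight.
- **Threshold wording.** The payment rule requires women to "attest to completion of >80% of the study exercises", while the attestation and the SAP accept 80% itself. This is a payment condition, not an analysis definition. No whole number of sessions equals exactly 80% of 14, 21, 112 or 168, so strict and non-strict versions classify every session count alike. They can differ only for a woman who attests to exactly 80%.
- **A biased comparison between arms.** The leva cut-off is looser, but the compliance objective covers the leva arm only and no passage names a between-arm comparison of compliance, though the general wording of SAP 3.5 could cover one.
- **A large shift in the leva rate.** That would need reports clustered at 11, which the documents neither show nor exclude.

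**Conclusion.** The point holds in a limited form. The leva cut-off in SAP 3.3 is a wrong threshold for a stated objective: 78.6% under a rule that requires 80%. That much is arithmetic and rests on no assumption. The number affected is not known. The estimate of 2 to 6 of 30 depends on the assumed normal shape, SD 2 and a mean from 8 to 13; means further from 11 would give fewer, and heaping of reports at 11 could give more. Efficacy results are untouched.

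The conflict over the Kegel schedule is a separate and real contradiction. It can reclassify any control doing 12 to 16 sessions per week, a wider band than the single leva value. The documents do not settle which schedule applies, and this review does not choose.

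**What to change.** In SAP 3.3, replace the two rounded weekly counts with one rule for both arms: sessions reported divided by sessions prescribed, at least 0.80, without rounding the threshold. Eleven of 14 is then not compliant. On leva device totals, the requirement is 90 of 112 sessions. A fixed weekly cut-off of 12 is not equivalent: it amounts to 12 × 8 = 96 of 112 (85.7%), which would fail women with 90 to 95 sessions and would be stricter than the Kegel 81.0%.

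Reconcile the Kegel arm text and Visit Content in Protocol 8.1, Protocol 8.4.1 and SAP 3.3 on the Kegel schedule before applying the ratio there. Controls have no device record, so their ratio must rest on recall.

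The SAP describes a trial that has already ended, so the change belongs in the analysis rule. The SAP should also state how attestations already collected map to it, given that leva women were told about 11 and Kegel women were given both a twice-daily wording and about 17.

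The cost is a few sentences. The reported leva compliance rate may be slightly lower.

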7.2 Study Endpoint(s)

Efficacy:

Efficacy, the primary outcome will be evaluated following 8- weeks of treatment at an in-person interview by study personnel blinded to randomization, and then again by phone and email or mail at 6- and 12- months. Two validated measures will be used to evaluate primary outcomes. First, the patient global impression of improvement (PGI-I), with success was defined as a response of “much better” or “very much better”. Second, the Pelvic Floor Distress Inventory (PFDI-20) urinary distress inventory (UDI-6), with success defined as the absence of bothersome stress incontinence symptoms as indicated by an answer of “no” to the stress incontinence subscale items OR a response of “yes” but with a bother of “not at all” or “somewhat. Other responses will not be considered successes.

Safety and Tolerability:

1. Reported Adverse Events (AEs) and Serious Adverse Events (SAEs)

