8 INVESTIGATIONAL PLAN

8.1 Overall Study Design and Plan

- A prospective, nested, randomized multicenter controlled study to evaluate the efficacy of using the leva® Plus Digital Pelvic System to perform PFME in comparison to Kegel exercises.
- Subjects will be patients referred to a Urogynecologist's office for evaluation.
- Following completion of baseline screening and consent, patients will be randomized by study coordinators at the baseline office visit using an automated randomization system.
- Patient population: women with moderate to severe SUI or stress-dominant mixed urinary incontinence.
- The duration of participation is 8- weeks, with expected post-intervention follow up surveys 6- and 12-months after study terminus.
- Up to 75 participants per site will be enrolled for a total of 225 subjects in the trial.

STUDY ENROLLMENT

The women interested in the study will be screened for participation based on inclusion/exclusion criteria and the MESA questionnaire identifying stress or stress-dominant mixed incontinence, and the UDI-6 (score > 25).

Screening visit: The study will be explained by the study staff and the consent will be reviewed with prospective participants.

- 1) The following questionnaires will be administered:
 - a. MESA
 - b. UDI-6
- 2) Pelvic exam will be performed including:
 - a. POP-Q (acceptable to report from an exam within 3 months of baseline)
 - b. Pelvic floor muscle assessment (Brink Scale) (may be performed at baseline or screening visit (if screening < 3 months prior to baseline)
- 3) If the eligibility requirements are met, patients should be given a 3-day voiding diary (acceptable if reported within 3 months of baseline visit)

The consent will be obtained by the licensed physician investigators or study assistants. Study participation will be entirely voluntary.

STUDY PROCEDURES

Once patients have undergone the appropriate screening evaluation, met criteria for study participation, and provided informed consent, subjects will be randomized to one of two study arms. The "Kegel" arm will involve patient education and performance of Kegel exercises, the current standard of care. The "Leva" arm of the study will undergo patient education and performance of pelvic floor muscle exercises using the Leva system. Subjects in the "Leva" arm will be sub-randomized to one of two long term follow up plans, follow up without reminders or follow up using automated reminders by text message.

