8.3 Selection of Study Population

8.3.1 Inclusion Criteria

Subjects must fulfill all the following inclusion criteria to be eligible for participation in the study, unless otherwise specified:

- Female.
- Capable of giving informed consent.
- Self-reported stress-type UI symptoms of \geq three months duration
- Diagnosis of stress predominant urinary incontinence based on MESA stress symptom score greater than MESA urge symptom score (percent of total possible urge score).
- UDI-6 score \geq 25
- Willing to participate in the 8-week study with follow up at 6-and 12-months, refraining from the pursuit of treatment for Stress Urinary Incontinence using other modalities (i.e. will not wear a pessary, participate in pelvic floor PT or surgery) during the first 8- weeks.

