- **Pelvic Floor Disability Index (PFDI):** Obtain the mean value of all of the answered items within the corresponding scale (possible value 0 to 4) and then multiply by 25 to obtain the scale score (range 0 to 100). Missing items are dealt with by using the mean from answered items only. For the summary score, add the scores from the 3 scales together to obtain the summary score

(range 0 to 300). This can be reported as a continuous variable or may be categorized depending on distribution of the data. For the primary outcome, “No urinary distress” will be defined as a raw score of 2 or less on all six indicators in the UDI-6 subscale. Raw scores of greater than 2 will be considered reports of distress.

- **Pelvic Organ Prolapse/Urinary Incontinence Sexual Questionnaire (PISQ-IR):** Validated scoring available from Constantine, M.L., Pauls, R.N., Rogers, R.R. et al. *Int Urogynecol J* (2017) 28: 1901.
- **McGill Pain Questionnaire:** The level of pain for each word can be reported as None, Mild, Moderate, Severe. Collapsing of responses is also possible (pain vs. no pain, no/mild pain vs. moderate/severe pain). Reporting of the visual analogue scale will depend on data recording. Reports of pain location will need to be manually reviewed and categorized.
- **Self-Efficacy Scale for Practicing Pelvic Floor Exercises (SESPPFE):** Sum all of the scores to calculate total score for the scale. This can be reported as a continuous variable or may be categorized depending on distribution of the data.
- **Patient Global Impression of Improvement (PGI-I) Scale:** This is only a single question and will be dichotomized as improvement (“very much better” or “much better”) vs. no improvement (all other non-missing answers).
- **Patient Global Impression of Severity (PGI-S) Scale:** This is only a single question and can be reported as is.
- **World Health Organization Disability Assessment Schedule (WHODAS):** Two options are available for scoring the WHODAS. The first is a simple summary score as a continuous variable. The second option is to use the available coding provided by the WHO (http://apps.who.int/iris/bitstream/handle/10665/43974/9789241547598_eng.pdf;jsessionid=680B7F5F1FC5DE085FA4DCFD302F1176?sequence=1). A score of 17 or greater constitutes significant disability.

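### SAP 3.4 redefines the second primary outcome on all six UDI-6 items, where protocol 7.2 uses only the stress incontinence items, and does not say so

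*SAP*

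**What the plan says.** Protocol 7.2 names two measures for the primary outcome. The first is the PGI-I. The second comes from the UDI-6 part of the PFDI-20, and its rule opens thus: "success defined as the absence of bothersome stress incontinence symptoms as indicated by an answer of". Only the stress items are judged. A woman passes by denying the symptom, or by reporting it and grading the bother *not at all* or *somewhat*. Any other response is not a success.

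SAP 3.4 keeps the PGI-I rule unchanged. It renames the second outcome as no urinary distress and defines it as "a raw score of 2 or less on all six indicators in the Pelvic Floor Disability Index (PFDI-20") UDI-6 subscale. The PFDI scoring entry in the same section repeats the rule for the primary outcome: "raw score of 2 or less on all six indicators in the UDI-6 subscale". Of the PGI-I and UDI-6 outcomes together the SAP says "Both will be reported as the primary study outcome".

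The trial population is "women with moderate to severe SUI or stress-dominant mixed urinary incontinence" (protocol 8.1). The entry criterion in protocol 8.3.1 is "Diagnosis of stress predominant urinary incontinence based on MESA stress symptom score greater than MESA urge symptom score", together with a UDI-6 score of at least 25. No criterion limits bother on the non-stress UDI-6 items.

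**The concern.** The two documents define one of the two primary outcomes on different sets of items. The protocol asks whether stress leakage has stopped being bothersome. The SAP asks whether any urinary symptom on the UDI-6 is still bothersome. The objective in both documents concerns stress-predominant incontinence.

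An analyst who follows the SAP will report as primary a variable that protocol 7.2 does not define. The same variable enters two further analyses:

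- the combined efficacy outcome (SAP 3.4 and 3.5);
- the comparison of primary outcomes between leva users who did and did not call about technical problems (SAP 3.2.2), which is part of the feasibility assessment.

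The SAP is dated August 2019 and describes enrolment and the 8 weeks of follow-up in the past tense. It does not say whether outcome data had been seen when the definition was written. Nothing suggests that they had, but a reader cannot rule it out.

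**Working it through.** **1. The definitions side by side**

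| | Protocol 7.2 | SAP 3.4 |
|---|---|---|
| Items | Stress incontinence items of the UDI-6 | All six UDI-6 items |
| Passing answer | *No*, or *yes* with bother *not at all* or *somewhat* | Raw score 0, 1 or 2 |
| Label | No bothersome stress symptoms | No urinary distress |
| Status | One of two primary measures | One of two primary outcomes |

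The cut-off appears unchanged: on an item scored 0 to 4, three passing answers fit raw scores 0, 1 and 2. Neither document prints the codes, so this is an inference. What clearly changes is the set of items.

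**2. Is the change disclosed?** SAP section 2 refers to the protocol for design and visits. The SAP acknowledges the early stop, the pilot status and the shortfall in sample size and follow-up. It says nothing about a changed endpoint.

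**3. Can the two rules disagree for an eligible woman?** Suppose that at week 8 all her stress items are 0, one non-stress item is 3 and the others are 0. The SAP's scale score uses this rule: "Obtain the mean value of all of the answered items within the corresponding scale (possible value 0 to 4) and then multiply by 25". Her score is (3/6) × 25 = 12.5. She is a protocol success, and the single 3 makes her an SAP failure.

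**4. What is certain.** If the cut-offs match, every woman who passes on six items also passes on the stress items. The SAP success rate is therefore no higher than the protocol rate in either arm.

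**5. The plan's own figure.** The only sample size (protocol 10.1.1) is for the PGI-I: 30% vs 50%, two-sided 0.05, power 0.80.

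n = [1.96·√(2·0.4·0.6) + 0.8416·√(0.3·0.7 + 0.5·0.5)]² / 0.2² = 93 per arm, as stated. It does not depend on the UDI-6 definition.

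**6. Illustration of the effect on the comparison.** The documents give no UDI-6 success rates, so these inputs are assumptions:

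- stress-item success of 30% (Kegel) and 50% (leva), borrowed from the PGI-I planning rates;
- q, the probability that a stress-item success also passes every non-stress item, so that SAP success = stress-item success × q;
- n = 30 per arm, as enrolled.

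SE(log RR) = √[(1−p₁)/(n·p₁) + (1−p₂)/(n·p₂)], and the 95% CI is RR × exp(±1.96·SE). For q = 1, SE = √(0.7/9 + 0.5/15) = 0.333 and RR = 0.50/0.30 = 1.67.

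| q Kegel / q leva | Rates | RR (95% CI) |
|---|---|---|
| 1 / 1 | 30% vs 50% | 1.67 (0.87–3.20) |
| 0.8 / 0.8 | 24% vs 40% | 1.67 (0.77–3.61) |
| 0.6 / 0.6 | 18% vs 30% | 1.67 (0.65–4.26) |
| 0.6 / 0.8 | 18% vs 40% | 2.22 (0.92–5.36) |
| 0.8 / 0.6 | 24% vs 30% | 1.25 (0.54–2.89) |

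For the three equal-q rows, power (pooled null variance, two-sided 0.05) is 35%, 26% and 19%. With equal q only precision is lost. With unequal q the risk ratio can move either way.

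**The case against.** The strongest reply is that little rests on this result. The SAP presents itself as a secondary analysis of a pilot stopped at 60 women. Its objectives are feasibility, technical issues and compliance, and it asks for cautious reporting. That lowers the inferential stakes. However, SAP 3.5 still tests at two-sided 0.05 and estimates risk ratios to judge efficacy, and a caution about sample size does not tell a reader that an endpoint has changed.

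Second, only one of two measures moves, and the protocol is not uniform about what is primary. Section 10.1.1 names the PGI-I alone, and the flow chart in section 4 lists PFDI, PGI-I and PGI-S. That is true, but section 7.2 is the only place where the protocol defines UDI-6 success.

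Third, the numerical illustration rests on borrowed and assumed inputs, and power at 30 per arm is already low with q = 1. This stands. The table shows only that the direction is open. Likewise, the low score of 12.5 does not show which item set is right: a woman scoring 2 on all six items has a scale score of 50 and passes the SAP rule.

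Fourth, SAP 3.1 says available scoring for validated instruments will be used, so item codes can be found elsewhere. That is a fair point about the codes, and listing them is a secondary request. It does not settle which items count.

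Finally, the sponsor could keep the six-item rule and justify it. That would end the silence, but it would leave a primary outcome redefined in a document that already reports enrolment and follow-up as done.

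**Conclusion.** The concern holds. The SAP's second primary outcome is not the one in protocol 7.2, and the change is neither stated nor justified. It should be corrected before any result is reported as primary.

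That conclusion rests on the text alone. That the SAP success rate can only be equal or lower in each arm also requires that raw scores 0 to 2 correspond to the protocol's passing answers. The number of women reclassified cannot be derived from the documents, and neither can the direction of any shift in the treatment comparison. The risk ratios of 1.25 to 2.22 are illustrations under assumed rates, not estimates.

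**What to change.** - In both places in SAP 3.4 (the efficacy definition and the PFDI scoring entry), define the second primary outcome on the UDI-6 stress incontinence items, as in protocol 7.2.
- Name those items and list the raw scores for *no*, *not at all* and *somewhat*.
- Build the combined outcome (SAP 3.4 and 3.5) and the technical-issues comparison (SAP 3.2.2) from that definition.
- Keep the PGI-I and the UDI-6 stress outcome as the two primary measures. Report the six-item version as a labelled supportive outcome.
- If the sponsor nevertheless intends the six-item rule as primary, the SAP must at least state the change, the reason, and whether it was made before outcome data were seen.

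The cost is wording in two places, a short list of items and codes, one recoded variable and one extra reported outcome. The PFDI is already collected at week 8, so there is no added burden for participants.
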